**Table 6-2 Sample Size**

	True Success Rate for Barrel ® VRD Device							
% Raymond Grade 1	38%	39%	40%	41%	42%	43%	44%	45%
Sample Size	177	145	123	107	92	80	71	62

Principal [name] and the clinical team agree that there is potentially an advantage to the Barrel® VRD device and thus a 41% success rate is the expected performance. Assuming a 10% dropout rate, the number of subjects required to be treated for the study is 119. The total number of subjects enrolled will be 159 to account for up to 25% of subjects who consent for the trial and withdraw prior to treatment or are determined to be ineligible.

### 6.4 Endpoint Analysis and Reporting of Results

All statistical analyses will be performed using SAS Version 9.2 or higher or other valid statistical software. Descriptive summary statistics will be provided for endpoints along with 95% confidence intervals as appropriate. Subject data listings and tabular and graphical presentations (e.g., bar graphs, pie charts, line graphs) of results will also be provided.

### 6.5 Statistical Analysis Sets

The primary analysis set will be based on the intention-to-treat (ITT) population set. For this study, all subjects who meet the study entry criteria, sign the written informed consent (enrolled), and undergo attempted delivery with the Barrel VRD will be counted in the primary analysis set of ITT.

Analysis will also be performed on the per-protocol population set, defined as all subjects included in the ITT population set who have complied with the protocol without major protocol deviations, and have completed the 12-month angiographic evaluation.

The primary analyses for both the safety and effectiveness endpoints will be based on the observed data.

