## 6.2 Primary Analysis

The goal of the primary analysis will be to demonstrate that the Barrel® VRD device performs better than the combined historical control treatments for complete occlusion rate at 12 months. The hypothesis to be tested is:

$$H_0: \pi_B = \text{HC} \text{ versus } H_A: \pi_B > \text{HC}$$

Where  $\pi_B$  is the proportion of successful outcomes for the Barrel® VRD device and HC is the combined overall historical control success rate. Success is defined as a subject with a Raymond Grade of 1 (100% occlusion) at 12 months  $\pm$  8 weeks in the absence of retreatment, parent artery stenosis (> 50%), or target aneurysm rupture. This hypothesis will be tested using an exact one sample binomial test at ( $\alpha = 0.025$ ). Exact 95% confidence intervals will be constructed.

The meta-analysis analysis mentioned above provides an overall estimate for historical control success rate of 42.48% with a 95% confidence interval of (31.90%, 53.06%).

Although the meta-analysis provides the basis for deriving a historical control success rate, it does not allow exact comparison due to the author-evaluated Raymond Grades used in the studies versus the proposed core laboratory grade reporting. Moreover, the reported rates in the published literature do not take into account patients lost to follow-up in their final calculation of occlusion rates. Conversely, the Barrel study employs a more stringent intent-to-treat (ITT) methodology that treats those patients lost to follow up as treatment failures. A review of the literature shows that onsite angiographic evaluators report 20 to 60% higher Raymond Grade success rates than those reported by core laboratories. Rezek et al. (2013) states “Core laboratories tend to report higher rates of unfavorable outcomes compared with self-reporting centers. Indeed, the rate of unfavorable outcomes was 43.6% greater in core laboratories compared with noncore laboratory studies.” McDougall CG et al. (2014) states, “in 36% of cases, the local investigators reported a better degree of occlusion than did the core laboratory.”

Unfortunately only one paper, Rezek et al. (2014), provided sufficient detail of the operator and core laboratory

results, in a population that is representative of the patient population that is proposed in the protocol, to allow statistical analysis of the difference.

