## 6.6 Analysis of Primary Safety Endpoint

The primary safety endpoint is defined as the incidence of neurological death or major ipsilateral stroke (National Institute of Health Stroke Scale [NIHSS] increase of  $\geq 4$  for  $>24$  hours) at any time during the follow-up period (12 months  $\pm$  8 weeks). Total number and frequency of subjects with neurological death or major ipsilateral stroke will be presented with two-sided 95% confidence intervals of the rate.

The primary safety endpoint will be met if the upper bound of the confidence interval is  $\leq 15\%$ . Table 6-3 below summarizes the clinical outcomes of the three studies from the background that specifically address endovascular treatment of wide-necked basilar and MCA aneurysms. Information about these studies is summarized in Section 5, “Background for Proposed Trial”. A complication rate was identified for each article by including events which could indicate stroke (i.e., thromboembolic events, ischemic events, artery dissection, hemorrhage, aneurysm rupture, and cranial nerve palsy). The overall weighted average of the incidence rate derived from the meta-analysis of these three trials was 13%. This provides the basis for selecting 15% for the primary safety endpoint of the Barrel study.

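### The supportive per-protocol set requires a completed 12-month angiogram and is not limited to efficacy, so deaths before imaging and failed implants are always excluded and its results lean favourable

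*Protocol*

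**What the plan says.** Section 6.5 first fixes the main set: "The primary analysis set will be based on the intention-to-treat (ITT) population set". That set is everyone eligible and consented in whom delivery of the device was attempted. The section then adds: "Analysis will also be performed on the per-protocol population set", made up of ITT subjects "who have complied with the protocol without major protocol deviations, and have completed the 12-month angiographic evaluation". It does not say which endpoints this second analysis covers. It closes with "The primary analyses for both the safety and effectiveness endpoints will be based on the observed data".

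Section 6.6 defines the primary safety endpoint as "the incidence of neurological death or major ipsilateral stroke" at any time in follow-up (12 months ± 8 weeks). The criterion is an upper 95% confidence bound of at most 15%, and no interval method is named. Section 6.2 defines efficacy success as Raymond Grade I at 12 months with no retreatment, no stenosis of the parent artery above 50% and no rupture of the target aneurysm, and tests it with an exact binomial test. Section 6.3 requires the lower 95% limit to exceed 28%.

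Sections 12.6.5, 12.6.7 and 12.6.8.2 all send a subject with attempted delivery but no implant out of the study after the 30-day visit.

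**The concern.** A per-protocol set should select on adherence. This one also selects on something that happens after treatment: being alive, in the study and imaged at about 12 months. Two groups of ITT subjects can never satisfy it, namely those who die before the angiogram and those in whom the implant failed. The first group includes a component of the primary safety endpoint. The second consists of subjects in whom the device did not achieve its purpose.

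The purpose of a second analysis set is to show whether the main result is robust. If the set sheds its worst outcomes by definition, a per-protocol result better than the ITT result may be selection and nothing else. For safety the requirement also has no function, because neither death nor stroke is ascertained by a 12-month angiogram.

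**Working it through.** **The plan's own figures.** Inputs from sections 6.2 and 6.3: null rate 28%, expected rate 41%, one-sided alpha 0.025, 80% power, exact binomial test. At n = 107 the test rejects at 40 or more successes, with exact alpha 0.0221 and power 0.804. Then 107/0.90 = 118.9, giving 119 treated, and 119/0.75 = 158.7, giving 159 enrolled. All three figures reproduce, so 119 is used as the ITT size below.

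**Who is excluded.**

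| Subject | In ITT? | In per-protocol set? |
|---|---|---|
| Dies before the 12-month angiogram | Yes | Never |
| Attempted delivery, no implant | Yes | Never (exits after day 30) |
| Retreatment, rupture, parent artery stenosis > 50% or non-fatal major stroke | Yes | Yes, if imaged and without a major deviation |
| Grade II or III at 12 months | Yes | Yes, unless there is a major deviation |
| Dies after an early in-window angiogram | Yes | Yes, unless there is a major deviation |

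**Illustration.** The protocol gives no expected number of deaths, failed implants or unimaged failures, so the counts are assumed. Everyone not removed is taken as imaged and free of major deviations. Limits are Clopper-Pearson 95%: for x events in n, lower = Beta(0.025; x, n − x + 1) and upper = Beta(0.975; x + 1, n − x).

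*Safety, bound 15%.* Each removed death leaves both numerator and denominator.

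| Set | x/n | Rate | Upper limit | Result |
|---|---|---|---|---|
| ITT | 11/119 | 9.2% | 15.9% | misses |
| 1 death removed | 10/118 | 8.5% | 15.03% | misses |
| 2 deaths removed | 9/117 | 7.7% | 14.1% | meets |

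For reference, 10/119 has upper limit 14.9%, so 11 is the smallest ITT count that misses. Event-free subjects without imaging also leave the set and shrink the denominator, which works the other way. With 2 deaths removed, the bound is still met after 7 more such losses (117 − 7 = 110; 9/110, upper limit 14.96%) but not after 8 (9/109, 15.10%).

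*Efficacy, goal 28%.* Each removed failure leaves the denominator only.

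| Set | x/n | Rate | Lower limit | Result |
|---|---|---|---|---|
| All treated | 42/119 | 35.3% | 26.8% | misses |
| 6 unimaged failures removed | 42/113 | 37.2% | 28.3% | meets |

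The first row counts all 119 as observed, with the six as known failures. Section 8.1.1 still prints 23% as the efficacy bound; against that figure both rows would meet it. The comparison uses the 28% of section 6.3.

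**The case against.** The strongest reply is that nothing is decided on this set. ITT is primary, and the criteria in sections 6.3 and 6.6 do not mention the per-protocol population. That stands: the point concerns a supportive analysis.

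Second, section 6.5 does not say that safety will be analysed per protocol; an angiogram requirement suits an efficacy set, and the choice of endpoints could be settled in the SAP. In part this stands. But the protocol fixes the membership rule itself and places no limit on its use, so a safety analysis on this set is open as written.

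Third, a completers' analysis of efficacy beside an ITT analysis is common practice. That also stands, provided it is labelled as such. It does not rescue the safety use.

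A reader might infer more than the text supports:

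- That every neurological death drops out. A death after an early in-window angiogram, but before follow-up ends, would stay in.
- That many other failures drop out by construction. Retreatment, rupture, stenosis and non-fatal stroke do not bar imaging, and section 12.6.5 asks for 12-month angiographic assessment in all implanted subjects. Only deaths before imaging and failed implants are certain to be lost.
- That the set is useless for both endpoints. That is too strong for efficacy.

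Finally, the size of the effect rests on assumed counts. With one death among 11 events, the safety conclusion does not change.

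**Conclusion.** The definition is badly fixed in the protocol, and the point holds in limited form. Deaths before the 12-month angiogram and all failed implants are excluded by rule; other failures are excluded only when unimaged, in numbers that the protocol does not allow one to derive. Any per-protocol safety rate loses nearly all of its fatal component and is biased low, and per-protocol efficacy is biased upward.

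Near the decision bounds, a small number of exclusions is enough to reverse the apparent result: two deaths among 11 safety events, or six unimaged failures with 42 successes. This assumes exact limits (section 6.6 names no method), 119 ITT subjects, the 28% goal and few other losses.

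The formal success criteria do not rest on this set. One related matter does touch them: section 6.5 puts the primary analyses on observed data, whereas section 6.2 says that subjects lost to follow-up count as failures. If unimaged subjects also leave the primary efficacy denominator, the ITT and per-protocol analyses could lean the same way, and their agreement would say little about robustness.

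**What to change.** In section 6.5, define the set separately for each endpoint.

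- **Safety:** ITT subjects without major protocol deviations, with no angiogram requirement, so that all neurological deaths and major ipsilateral strokes among them count.
- **Efficacy:** ITT subjects without major protocol deviations who either completed the 12-month angiogram or, before it, had target aneurysm rupture, retreatment, documented parent artery stenosis > 50%, neurological death or a failed implant. Count the latter group as efficacy failures. If the present rule is kept instead, call it a completers' analysis and confine it to efficacy.

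The two lists must stay apart. Stroke, for example, is a safety event but not an efficacy failure under section 6.2.

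The cost is a few sentences and slightly less favourable per-protocol rates. Failed implants would enter the safety set with follow-up only to the 30-day visit, as they already do in ITT. No additional data are needed.

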### 12.6.5 Follow-Up (30-day, 180-day, and 12-month)

The following assessment will be completed at the specified time points below. All visits should be completed by study subjects with successful implant of the Barrel VRD. Subjects that underwent attempted delivery with the Barrel VRD, but were not implanted should complete the 30-day visit and be exited from the study.

- 30 Day  $\pm$  14 Days
  - Neurologic Evaluation
    - The Investigator is responsible for ensuring that the administration of the modified Rankin Score is conducted by a trained person with appropriate qualifications to perform these evaluations.
  - Details of any additional (subsequent) procedures or additional treatments
  - Description of adverse events, including the time of onset
  - Medication Usage
  - 30 day evaluations may be performed remotely via telephone if subject is not available for a visit to the study center.

- 180 Day  $\pm$  30 days
  - Neurologic Evaluation
    - The Investigator is responsible for ensuring that the administration of the NIHSS and modified Rankin Score are conducted by a trained person with appropriate qualifications to perform these evaluations.
  - Details of any additional (subsequent) procedures or additional treatments
  - Angiographic assessment (if done as standard of care)
    - Stenosis
    - Raymond grade
  - Description of adverse events, including the time of onset
  - Medication Usage
- 12 month  $\pm$  60 days
  - Neurologic Evaluation
    - The Investigator is responsible for ensuring that the administration of the NIHSS and modified Rankin Score are conducted by a trained person with appropriate qualifications to perform these evaluations.
  - Details of any additional (subsequent) procedures or additional treatments
  - Angiographic assessment
    - Stenosis
    - Raymond grade
  - Description of adverse events, including the time of onset
  - Medication Usage

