## 12.8 Adverse Event Reporting

All adverse events will be collected during the course of the study on the eCRFs.

Adverse event status will be evaluated throughout the study. These will include events occurring from the point of consent until a subject exits the study. Investigators must obtain all information available to determine the causality and outcome of the AE and to assess whether it meets the criteria for classification as a serious and/or unexpected event requiring notification to the Sponsor, regulatory agency, and as applicable, IRB/EC, within the specified reporting timeframe. AEs will be categorized using the definitions in **Section 12.8.1**.

All study AEs, as well as the treatment and follow-up required, should be documented in the subject's medical records and in the eCRF. All study AEs will be followed by the Investigator until resolution or until the end of the 12 month follow-up. A list of potential anticipated adverse events is provided in **Section 13**.

All relevant medical conditions reported at screening/baseline visit will be recorded in the medical history form, including any signs and symptoms related to the condition of intra-cranial aneurysm.

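### The 12-month primary safety rate is a simple proportion of observed data, while non-implanted subjects in its analysis set leave at day 30 and nothing handles incomplete safety follow-up

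*Protocol*

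**What the plan says.** **Endpoint and rule.** Protocol 6.6 (repeated in 8.1.1) defines primary safety as neurological death or major ipsilateral stroke at any time over 12 months ± 8 weeks. The estimator is a simple proportion: "Total number and frequency of subjects with neurological death or major ipsilateral stroke will be presented with two-sided 95% confidence intervals of the rate". The decision rule is "The primary safety endpoint will be met if the upper bound of the confidence interval is" at or below 15%.

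**Analysis set.** Under 6.5, eligible, consented subjects who "undergo attempted delivery with the Barrel VRD will be counted in the primary analysis set of ITT". The same section adds: "The primary analyses for both the safety and effectiveness endpoints will be based on the observed data".

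**Follow-up.** Section 12.6.5 states: "Subjects that underwent attempted delivery with the Barrel VRD, but were not implanted should complete the 30-day visit and be exited from the study". Sections 12.6.7 and 12.6.8.2 repeat the day-30 exit. On the collection of adverse events, 12.8 says: "These will include events occurring from the point of consent until a subject exits the study". Under 12.6.8.1, data collected up to a withdrawal are kept and analysed.

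**Missing data.** The multiple imputation in 6.10 is introduced for the efficacy endpoint. No provision covers incomplete safety follow-up.

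**The concern.** A non-implanted subject belongs to the primary analysis set for a 12-month endpoint but is observed for about one month of it by rule. Withdrawn and lost subjects are likewise observed only in part. If such a subject has had no event, the 12-month safety status is unknown, and the protocol does not say how that person enters the proportion.

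Two readings are open, and neither gives a sound 12-month rate:

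- **All attempted deliveries in the denominator.** Unobserved months count as event-free, so the rate is biased downward. The subjects with the shortest planned observation are those in whom the device could not be placed.
- **Only subjects with a known outcome.** Event-free early leavers drop out while early leavers with an event stay in, so the rate is biased upward.

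This is one of the two primary endpoints of a single-arm study and has a fixed pass/fail limit. As written, the denominator could be settled after the events are known. The day-30 exit is also a rule of the protocol itself: an analysis plan can define censoring, but it cannot recover strokes or deaths that were never collected.

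**Working it through.** **Inputs.** 119 treated or attempted and 107 evaluable after 10% loss (6 and 6.3); limit 15% on the upper bound of a two-sided 95% interval (6.6). Section 6.6 names no interval method. Exact limits are assumed here because 6.2 names them for efficacy; Wilson and Wald limits are shown as the range.

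**Step 1. Reproduce the plan's own numbers.** For an exact one-sample binomial test of 28% against 41% at one-sided 2.5%, n = 107 with success at 40 or more gives a type I error of 0.0221 and power of 0.804, matching Table 6-2. Then 107 / 0.90 = 118.9, so 119 treated, and 119 / 0.75 = 158.7, so 159 enrolled. The 107 is therefore the evaluable number for efficacy. It serves below only as a lower illustration.

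**Step 2. Denominator under each reading.** With all attempts kept, N = 119. With event-free leavers dropped, N = 119 − (event-free early leavers). If 12 subjects leave early (119 − 107) and m of them had an event first, N = 107 + m. An early leaver with an event, including anyone who dies a neurological death, adds to 107.

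**Step 3. Exact upper limit.** The formula is U = Beta quantile(0.975; x + 1, N − x) for x events in N subjects.

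| Events | N | Exact upper limit | ≤ 15%? |
|---|---|---|---|
| 10 | 119 | 14.91% | yes |
| 10 | 118 | 15.03% | no |
| 10 | 107 | 16.52% | no |
| 9 | 119 | 13.87% | yes |
| 9 | 110 | 14.96% | yes |
| 9 | 109 | 15.10% | no |
| 9 | 107 | 15.37% | no |
| 8 | 107 | 14.20% | yes |
| 11 | 119 | 15.94% | no |

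With 10 events, dropping a single event-free leaver reverses the result. With 9 events, it takes ten (119 − 109). In the 12-leaver case, 9 events fail if m is 0, 1 or 2 (N of 107 to 109) and pass if m is 3 or more (N of 110 upward).

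**Step 4. Other interval methods.**

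| Events | Wilson, N = 119 | Wilson, N = 107 | Wald, N = 119 | Wald, N = 107 |
|---|---|---|---|---|
| 9 | 13.75% | 15.22% | 12.31% | 13.67% |
| 10 | 14.78% | 16.35% | 13.39% | 14.86% |
| 11 | 15.80% | 17.48% | 14.45% | 16.03% |

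Between 119 and 107, Wilson flips at 9 and 10 events, as the exact method does. Wald flips only at 11. Each method has an event count at which the denominator decides; which count it is depends on the method.

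**Step 5. The interval also matters for a Kaplan-Meier estimate.** Take 10 events in 119 with no censoring before the last event. Then S = 1 − 10/119 = 0.9160, ln S = −0.0878 and the standard error of ln S is √(10 / (119 × 109)) = 0.0278.

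- Plain Greenwood: 0.0840 + 1.96 × 0.9160 × 0.0278 = 13.39%, met.
- Log-log: 1 − S^exp(1.96 × 0.0278 / 0.0878) = 15.06%, not met.

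**The case against.** **The conventional reading.** The best defence is that 6.5 and 6.6 together describe the usual device-trial incidence: events observed at any time, over all attempted deliveries, with pre-withdrawal data retained under 12.6.8.1. Denominator detail and interval method are often left to the analysis plan. Part of this stands: that reading is natural, and an interval method missing from a protocol would be no finding alone. But the observed-data sentence sits in the same section as the ITT definition, and the summary of changes (4.1) explains it as an analysis of observed cases, which points to the smaller denominator. Even on the conventional reading, months nobody observed count as event-free.

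**Inferences the documents do not support.**

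- A reader might conclude that 107 is the alternative safety denominator, so that 9 or 10 events simply fail on it. The protocol never offers 107 for safety. It would apply only if exactly 12 subjects left early and every subject with an event completed 12 months, which no neurological death can do. Under Wald limits, 9 and 10 events pass on both numbers.
- A reader might assume that failed attempts push the denominator well below 107. The protocol gives no failed-attempt rate and does not say whether the 10% loss already includes them.
- A reader might see a flat contradiction within 12.8, which also says "All study AEs will be followed by the Investigator until resolution or until the end of the 12 month follow-up". That sentence governs how long a reported event is followed; the other governs which events are collected. They clash only for an event still unresolved when a non-implanted subject exits. This is a minor wording point.

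**The deliberate exit.** The summary of changes presents the 30-day visit as a safeguard to secure adequate safety follow-up of non-implanted subjects. That explains the visit. It does not reconcile a one-month observation with a 12-month endpoint in the same analysis set.

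**Conclusion.** The point holds as a conflict within the protocol. A 12-month safety proportion is computed in a set that includes subjects whose observation ends at about day 30 by rule, with no method for incomplete safety follow-up. The bias is downward if early leavers stay in the denominator and upward if only the event-free ones are removed.

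The effect on the decision is confined to a narrow band of event counts near the 15% limit. Under exact limits that band is 9 and 10 events: at 10, one dropped subject suffices; at 9, ten are needed. Under Wald limits, comparing 119 with 107, it is 11 events. These figures rest on an assumed interval method and on 119 treated subjects. The number of early leavers, and how many of them have events, cannot be known from the protocol. This should be corrected, but it does not show that the safety conclusion would be wrong.

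**What to change.** - **Section 6.6.** Estimate the 12-month rate of neurological death or major ipsilateral stroke by Kaplan-Meier in all attempted-delivery subjects, censoring event-free early leavers at last contact. Compare the upper limit of one named two-sided 95% interval, for example log-log, with 15%. The interval must be fixed in advance, since Step 5 shows that it can decide the result too.
- **Sensitivity analyses.** Report events over all ITT subjects, and events over completers plus subjects with events.
- **Sections 12.6.5, 12.6.7 and 12.6.8.2.** Reconcile the day-30 exit with the endpoint by adding one telephone or record check at 12 months, for stroke and death only, in non-implanted subjects. No angiogram is needed. Without this check, Kaplan-Meier must assume that failed-attempt subjects censored at day 30 carry the same later risk as the rest, which is doubtful.
- **Section 12.8.** Align the wording on following adverse events with the exit rule. This is minor.

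The cost is a protocol amendment and a few extra contacts. The estimated rate may come out slightly above events/119. With log-log limits, 10 events among 119 subjects would narrowly miss, where the exact limit on 119 would pass.

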Despite substantial progress over the past decade, endovascular treatment of bifurcating aneurysms remains a significant challenge. Despite the lack of independent adjudication, a composite analysis (all complete occlusions divided by the total number of patients), of the above reviewed modern studies demonstrate only a 42% overall complete occlusion rate at follow-up. The mean and standard deviation of all three studies (treating each study as a single entity) is 43% and 3.5%, respectively. Again, it is worth noting that all of these studies were retrospective and un-adjudicated, significant contrasts to the proposed prospective adjudicated study, and a methodology well demonstrated to overestimate successful occlusion rates and underestimate complication rates. However, these data are the best available for this disease state.

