**Table 6-1 Meta-Analysis for Historical Control**

Study	Number of Aneurysms in the Trial	Number of Bifurcation Aneurysms in the Trial	Number of Wide-Necked Aneurysms in the Trial	Mean Age	Number of Women	Follow-up Time (Months)	Number with Angiographic Follow-up	Number of Raymond Grade I at Follow-up	% of Raymond Grade I of those Followed-up	% of Raymond Grade I of Cohort
Fargen 2013	45	45 (100%)	45 (100%)	57.9	31 (69%)	9.8	30	18	56%	40% (18/45)
Spiotta 2011	19	19 (100%)	19 (100%)	57.4	14 (74%)	16	17	9	52.90%	47% (9/19)
Zhang 2014	23	23 (100%)	23 (100%)	51.2	12 (51%)	13.5	16	10	62.5%	43% (10/23)
Total	87	87 (100%)	87 (100%)		57 (66%)	12.1	63	37	57.1%	42.5% (37/87)

The estimation of the rate of the primary endpoint derived from the three referenced studies, using the weighted proportion and its standard error (SE), was calculated using the following formula:

$$\hat{P} = \frac{\sum_i W_i p_i}{\sum_i W_i}, \text{ where } \hat{P} \text{ is the combined rate of complete occlusion;}$$

$p_i$  is the rate of complete occlusion in each referenced study;

$$W_i = \frac{1}{S_i^2}; S_i^2 = \frac{p_i(1-p_i)}{n_i}; \quad \text{where } n_i \text{ is the sample size of each reviewed study;}$$

$$SE(\hat{P}) = \sqrt{(\sum W_i)^{-1}}$$

and the 95% confidence interval (CI) is  $\hat{P} \pm 1.96 * SE(\hat{P})$ .

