An analysis of this data provided an adjustment of 36% between the operator results and the core laboratory results. This difference was consistent with the other published results. After adjustment, the estimated historical success rate for core lab results is 28%. The corresponding adjusted confidence interval is (23%, 33%).

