### 6.3 Sample Size Calculation

In actuality, the real objective of this study is to demonstrate that the Barrel® VRD is comparable to historical controls. Therefore the historical success rate of 28% was selected as the historical control value. The Barrel® VRD will be considered successful if its lower 95% confidence limit is greater than 28%.

Table 6-2 presents the sample size necessary to have an 80% power with a significance level of 2.5% for rejecting the null hypothesis in favor of the alternative when the true success rate for the Barrel® VRD is as specified. The hypotheses to be tested are:

$$H_0: \pi_B = 28\% \text{ versus } H_A: \pi_B > 28\%$$

Where  $\pi_B$  is the proportion of successful outcomes for the Barrel® VRD device.

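### The 28% control counts aneurysms without follow-up as failures while the primary analysis excludes them, the reverse of what Section 6.2 says, and the difference favours the device

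*Protocol*

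**What the plan says.** **Trial side.** Section 6.2 says the trial "treats those patients lost to follow up as treatment failures". Section 6.5 says "The primary analyses for both the safety and effectiveness endpoints will be based on the observed data". The sizing follows 6.5: Section 6 and Table 6-2 use 107 evaluable subjects out of 119 treated, after 10% loss. Section 6.10 adds multiple imputation under missing at random to assess the impact of missing efficacy data.

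**Control side.** Section 6.2 says "the reported rates in the published literature do not take into account patients lost to follow-up in their final calculation of occlusion rates". Table 6-1 gives two rates, one among those followed up and one for the whole cohort, and has a column headed "Number with Angiographic Follow-up" totalling 63 of 87. The rate carried forward is the whole-cohort one. Section 5 describes it as "a composite analysis (all complete occlusions divided by the total number of patients". Section 6.2 then lowers it for core-laboratory reading: "An analysis of this data provided an adjustment of 36% between the operator results and the core laboratory results". Section 6.3 concludes: "Therefore the historical success rate of 28% was selected as the historical control value".

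**The concern.** Section 6.2 presents the comparison as conservative, with a strict rule for the device and a lenient one for the literature. The rules actually in force run the other way. Patients without follow-up are non-successes in the control and are left out of the device's denominator.

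The primary pass or fail decision is at stake. A result can clear 28% partly because the denominators differ, and Section 6.2 would read that pass as the device outperforming the historical treatments. The two rules for lost patients can also give opposite verdicts on the same data.

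**Working it through.** **Reproducing the plan.** I used the exact one-sided binomial test at 2.5% with null 28%. With n = 107 the smallest passing count is 40: P(X ≥ 40 | 107, 0.28) = 0.022, and 39 gives 0.035. Power at 41% is P(X ≥ 40 | 107, 0.41) = 80.4%. This matches Table 6-2, and 107/0.9 rounds up to 119.

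**How the control treats missing follow-up.** Table 6-1 gives 18/45, 9/19 and 10/23. The inverse-variance pool is 42.48%, as printed, and the crude rate is 37/87 = 42.5%. The followed-up counts are 30, 17 and 16, total 63, so 24/87 = 27.6% have no angiographic follow-up. The same 37 successes serve both rates, so the 24 add none.

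Section 5 obtains 56% for the 45-aneurysm Y-stenting series by counting two deaths as failures (18/32 = 56%, whereas 18/30 = 60%). Two of the 24 therefore appear to be known failures. The followed-up control is then between 37/65 = 56.9% and 37/63 = 58.7%. The printed total is 57.1%.

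**Core-laboratory adjustment.** A 36% reduction is a factor of 0.64, giving 42.5% × 0.64 = 27.2%. The factor that yields exactly 28% is 28/42.48 = 0.659. Both are carried as a range. The followed-up control becomes 56.9% × 0.64 = 36.4% up to 58.7% × 0.659 = 38.7%.

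**Chance that a device equal to the control passes.** Let unfollowed control aneurysms occlude at a fraction f of the followed rate. The control rate is (37 + 24 × f × 37/63)/87, multiplied by 0.64 or 0.659. The last column is P(X ≥ 40 | 107).

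| f | Rate before adjustment | After adjustment | Chance of passing |
|---|---|---|---|
| 0 | 42.5% | 27.2-28.0% | 1-2% |
| 0.25 | 46.6% | 29.8-30.7% | 6-8% |
| 0.5 | 50.6% | 32.4-33.4% | 16-22% |
| 0.75 | 54.7% | 35.0-36.0% | 34-42% |
| 1 | 58.7% | 37.6-38.7% | 55-65% |

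Taking the followed-up control as 37/65, with the two deaths as failures, the last row becomes 36.4-37.5% and 45-55%.

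**On the control's own scale.** Take a device with 28% success when missing counts as failure, and 10% missing. Its observed rate is 0.28/0.9 = 31.1%, and P(X ≥ 40 | 107, 0.311) = 9.9%.

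**What the choice of rule changes.** With missing as failure and n = 119, 44 successes are needed: P(X ≥ 44 | 119, 0.28) = 0.021, and 43 gives 0.033. The minimum observed-case pass, 40/107, becomes 40/119 = 33.6% with exact lower limit 25.2%, a fail. With 12 missing, 40 to 43 successes pass under 6.5 and fail under 6.2. That range has probability 28% at a true observed rate of 41%.

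Power of the 44/119 rule depends on what 41% means. If it is the rate among observed subjects, the all-treated rate is 0.41 × 0.9 = 36.9% and power is 53%. If it already counts missing as failures, power is 84%. The protocol does not say which.

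**The case against.** Observed-case analysis was a deliberate Revision C choice with a stated rationale, so the Section 6.2 sentence looks like a leftover. That is probably so, but 6.2 still uses it to defend a control built on the whole-cohort rate. Multiple imputation under missing at random does not restore a missing-as-failure basis.

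A reader might infer that both 6.2 sentences are simply false. The documents do not support that. The sentence about the literature fits the followed-up percentages in Table 6-1. It misleads because the protocol carries forward the other column.

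A reader might also take 55-65% as the false-pass rate. That is the upper end. It assumes unfollowed control aneurysms occluded as often as followed ones. For the largest series, which supplies 15 of the 24, Section 5 considers it highly likely that the patients followed were the better-treated ones.

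Nor would missing as failure on both sides make the comparison like for like, because missingness is 27.6% in the control and 10% planned in the trial. If the followed-up control is 37.6-38.7% (37/63), a device equal to it has an all-treated rate of 33.8-34.8% and still passes 44/119 with probability 26-34%.

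Finally, trial success also requires no retreatment, no parent-artery stenosis above 50% and no rupture, whereas Table 6-1 counts Raymond Grade I. This may offset part of the advantage, but the documents give no figure. Section 6.3 also describes the real aim as comparability, which sits uneasily with the superiority goal in 6.2.

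**Conclusion.** Wrong as written. The current text gives two incompatible rules for patients lost to follow-up, and the denominators run opposite to the justification offered. The missing-data difference favours the device.

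Its size is not established. The chance that a device equal to the control passes runs from 1-2% to 55-65%, depending on the fate of unfollowed control aneurysms, and is 9.9% for a 28% device at the planned loss with missing as failure. These figures rest on the Table 6-1 counts, an adjustment factor of 0.64 to 0.659, and 107 observed of 119. Missingness could exceed 10%: subjects with an attempted but unsuccessful implant belong to the ITT set but exit at 30 days, and unless they are classed as failures they drop out of an observed-data analysis.

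A pass on observed data shows that a 28% performance goal was met. It does not by itself show better performance than the historical treatments.

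**What to change.** 1. Correct Section 6.2 so that it no longer says lost patients are failures, or that the control rate used ignores them.
2. Keep observed-case analysis as primary if that is intended, but pre-specify the missing-as-failure ITT result (44/119 needed) beside it.
3. State the followed-up control, 37/65 to 37/63, or about 36-39% after the core-laboratory adjustment, together with the range of pass probabilities above.
4. Describe a pass as meeting a 28% performance goal. Claim better performance than the historical control only if the missing-as-failure ITT analysis also passes.
5. State whether 41% is the rate among observed or all treated subjects, and give the matching power of the ITT test (about 53% or 84%).

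The cost is protocol wording, one more analysis and a less favourable claim. Making missing as failure the primary rule instead would be a larger change. It reverses the Revision C decision and, if 41% is the observed rate, leaves 53% power with 119 treated. About 222 treated would be needed to restore 80%.
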